### **9.2. Clarifications to Serious Adverse Event Reporting**

Death is an outcome of an SAE and not an SAE in itself. When death is an outcome, report the event(s) resulting in death as the SAE term (e.g., “pulmonary embolism”). If the cause of death is unknown, report “Death, unknown cause” as the SAE term.

### **9.3. Assessment of Causality**

All AEs occurring during this healthy-volunteer study will be presumed to be related to study drug unless occurring before the study therapy is initiated pending review by the SRC. AEs in the placebo group, although possibly related to a study procedure, cannot be related to rhu-pGSN unless the subject was mistakenly given the wrong treatment.

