#### **Minimum Sample Size Calculations**

Sample Size	TRUE underlying AE rate
6 (each rhu-pGSN dose level)	32%
8 (pooled placebo)	25%
12	18%
18	13%
24 (pooled rhu-pGSN doses)	10%

With each sample size presented in the table above, if zero AEs of a certain type (e.g., serious adverse events [SAEs]) are observed, one could be "90% confident" that the TRUE underlying incidence for that AE is at most the percentage indicated above. Thus with 24 healthy subjects, if no SAEs are observed, the probability is 90% that the true underlying incidence of SAEs in healthy subjects administered 5 doses of rhu-pGSN at 6, 12, 18, or 24 mg/kg of body weight is at most 10%.

No data will be excluded from the summary statistics and analyses, and missing data will not be imputed. All subjects given at least part of 1 dose of study drug will be included in the intention-to-treat analysis (full analysis set). As a sensitivity analysis, a per-protocol analysis set excluding subjects who missed doses and/or randomly discontinued the study before the primary Day 7 Visit will be analyzed. The expectation is that all analysis sets will be almost identical.

Descriptive summaries of the incidence of all AEs, drug-related AEs, SAEs, drug-related SAEs, AEs leading to discontinuation, and deaths will be provided. All AEs and drug-related AEs will be summarized by counts and proportions of subjects having an AE, each AE type, and an AE of each System Organ Class. Serious AEs will be summarized similarly. AEs leading to discontinuation of treatment or the study will be summarized. All reasons for any early discontinuations will be summarized.

Laboratory data will be summarized in relation to normal range values via counts and percentages of subjects below, within, and above the respective normal range, and by summary statistics (N, mean, median, standard deviation, minimum, maximum, 90% confidence intervals, etc.) for baseline, each observed time point, and change from baseline at each observed time point for continuous lab endpoints.

Demographics and medical history characteristics will be summarized via counts and percentages of subjects for categorical variables, and by N, mean and standard deviation or median and interquartile range, as appropriate for the distribution of continuous variables.

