## **9.7. Reporting Adverse Events**

All AEs, serious and nonserious, will be fully documented on the appropriate eCRF. For each AE, the Investigator must provide its duration (start and end dates or ongoing), intensity,

assessment of causality and whether specific action or therapy was required. All AEs occurring during this healthy-volunteer study will be presumed to be related to study drug unless occurring before the study therapy is initiated pending review by the SRC.

All AEs that occur from the signing of the informed consent form (ICF) until the first dose of study drug should be recorded on the AE eCRF page only if the event was related to a study procedure. All other AEs/findings prior to the first dose of study drug should be recorded as medical history on the applicable eCRF page. All AEs occurring from the first dose of study drug until 28 days after the last dose of study drug must be recorded on the AE eCRF.

All SAEs and Grade 4 AEs must be reported to the Sponsor within 24 hours of the Investigator's knowledge. All AEs occurring during this healthy-volunteer study will be presumed to be related to study drug unless occurring before the study therapy is initiated pending review by the SRC. This reporting should be done by faxing/emailing the completed SAE Report Form to the number provided on the SAE Report Form. After the EOS Visit, only new treatment-related SAEs need to be captured on the AE eCRF and reported to the Sponsor.

Investigators must follow subjects with AEs/SAEs until the event has resolved, the condition has stabilized, withdrawal of consent, the subject is lost to follow up or death OR until the EOS Visit, whichever occurs first. New and ongoing treatment-related SAEs should be followed beyond the EOS Visit. If the subject dies, this should be captured as the outcome of the AE unless no link between the AE and the subject death can be established, in which case the AE will be marked as ongoing and the death will be reported as a separate event.

If a subject is lost to follow up, this should be captured accordingly within the AE eCRF and on the follow up SAE report.

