#### 10.1.2. Data Collection and Analysis

Baseline characteristics, safety, PK, and development of ADAs will be summarized via summary statistics separately for each rhu-pGSN dose level; data for all placebo subjects will be pooled. Additional details will be provided in a separate Statistical Analysis Plan (SAP).

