## **10.4. Criteria for Evaluation and Statistical Methods**

### **10.4.1. Safety**

Descriptive summaries of the incidence of all AEs, drug-related AEs, SAEs, drug-related SAEs, AEs leading to discontinuation, and deaths will be provided. All AEs and drug-related AEs will be summarized by counts and proportions of subjects having an AE, each AE type, and an AE of each System Organ Class. Serious AEs will be summarized similarly. AEs leading to discontinuation of treatment or the study will be summarized. All reasons for any early discontinuations will be summarized.

Laboratory data will be summarized in relation to normal range values via counts and percentages of subjects below, within, and above the respective normal range, and by summary statistics (N, mean, median, standard deviation, minimum, maximum, 90% confidence intervals, etc.) for baseline, each observed time point, and change from baseline at each observed time point for continuous lab endpoints.

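### Does Section 9.3 force the placebo column of the drug-related adverse event summaries to zero?

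*Combined protocol and SAP*

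**What the plan says.** Section 9.3 (Assessment of Causality) contains two statements. The first is a presumption, held until the Safety Review Committee (SRC) has reviewed the event: "All AEs occurring during this healthy-volunteer study will be presumed to be related to study drug unless occurring before the study therapy is initiated". The second concerns placebo: "AEs in the placebo group, although possibly related to a study procedure, cannot be related to rhu-pGSN", the one exception being a subject who received the other treatment by mistake.

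Section 9.7 asks the Investigator to supply, for each AE, an "assessment of causality and whether specific action or therapy was required", and repeats the presumption. Section 7.11 keeps the site team blinded.

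Section 10.4.1 says: "Descriptive summaries of the incidence of all AEs, drug-related AEs, SAEs, drug-related SAEs, AEs leading to discontinuation, and deaths will be provided". The Synopsis copy adds the form of the display: "All AEs and drug-related AEs will be summarized by counts and proportions of subjects having an AE, each AE type". Section 10.1.2 presents results "separately for each rhu-pGSN dose level; data for all placebo subjects will be pooled", and it leaves further detail to a separate SAP. Neither 10.4.1 nor the abbreviation list defines *drug-related*.

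**The concern.** A table of drug-related events is normally read across its columns, with placebo showing how often blinded staff attribute ordinary events to treatment. Confinement, repeated blood draws and five IV pushes will produce some events in anyone.

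If *drug-related* is taken to mean related to rhu-pGSN, the second statement in 9.3 removes every placebo event from the table by definition. Any rhu-pGSN event left as related would then look like an excess over placebo, even with no drug effect. Section 10 does not say whether the Investigator's assessment, the presumption, the SRC's conclusion or the placebo statement supplies the tabulated value, so this reading is not expressly excluded.

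**Working it through.** **1. The plan's own figure for eight placebo subjects.** Placebo n = 4 cohorts × 2 = 8 (Section 10.2). Table 5 gives a 25% true rate for a 90% chance of at least one event. Check: 1 − (1 − 0.25)^8 = 0.8999, and the exact rate is 1 − 0.1^(1/8) = 25.01%. The figure reproduces. Table 5's reading of zero events in eight as a true rate of at most 25% would not apply to a zero set by definition.

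**2. Size of the artefact if the placebo statement were applied to the tables.** The documents give no expected AE rate and no share of events left as related, so these are assumptions:
- p = share of subjects with an AE, equal in all arms (no drug effect)
- k = AEs per affected subject
- s = chance that each AE is left as related, independent across AEs

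Subject-level rate q = p × (1 − (1 − s)^k). Expected counts are 24q for rhu-pGSN and 8q for placebo under one common rule. The last column is (1 − q)^8, the chance of 0/8 under a common rule.

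| p | s | k | q | rhu-pGSN | placebo, fixed | placebo, common rule | chance of 0/8 anyway |
|---|---|---|---|---|---|---|---|
| 0.50 | 1.0 | any | 0.500 | 12.0/24 | 0/8 | 4.0/8 | 0.4% |
| 0.50 | 0.2 | 1 | 0.100 | 2.4/24 | 0/8 | 0.8/8 | 43% |
| 0.50 | 0.2 | 2 | 0.180 | 4.32/24 | 0/8 | 1.44/8 | 20% |
| 0.25 | 1.0 | any | 0.250 | 6.0/24 | 0/8 | 2.0/8 | 10% |
| 0.25 | 0.2 | 1 | 0.050 | 1.2/24 | 0/8 | 0.4/8 | 66% |
| 0.25 | 0.2 | 2 | 0.090 | 2.16/24 | 0/8 | 0.72/8 | 47% |

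The displayed gap equals q. It is 50 points in the extreme case and 5 to 18 points when a fifth of events stay related. In the latter cases the fixed zero often matches what a common rule would have shown.

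**3. Whether the plan leads there.**
- *Who records causality.* The Investigator, for each AE (9.7), while blinded (7.11). A value recorded that way cannot depend on the arm.
- *Related to what.* The presumption in 9.3 refers to study drug. Section 9.7 starts AE collection at the first dose of study drug, and 10.3 defines the full analysis set by receipt of study drug. Both must include placebo subjects, or those subjects would have no collection window and no place in the analysis. Sections 7.1, 7.2 and 7.7 do separate study drug from placebo, but they deal with product description and supply.
- *What the placebo statement does.* It names rhu-pGSN, not study drug, and records a fact: a person who never received the product cannot react to it. It mentions neither coding nor tables.

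The placebo count under each possible source is therefore:
- blinded Investigator's call: anywhere from 0/8 up to the all-AE count
- presumption left standing for study drug in either arm: equal to the all-AE count
- placebo statement applied: 0/8

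The first two treat the arms alike, so the expected gap with no drug effect is 0. The third needs someone to recode relatedness by arm after unblinding, and no section describes that.

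**4. What depends on the answer.** The primary endpoint (4.2.1) ignores causality. The all-AE and all-SAE summaries come from the same sentence of 10.4.1 and carry the placebo background. The pause triggers in 5.2 and 5.3 count deaths, grades and SAEs. Resumption rests on the SRC's own judgement at the time, not on these tables. No between-arm test is planned.

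**The case for a change.** The best case for acting is that the protocol's wording points both ways. Section 9.3 is the only section devoted to causality, and it names rhu-pGSN as the thing an event can or cannot be related to. Section 7.1 describes study drug as rhu-pGSN alone. The expedited-reporting text in 9.7 uses *drug-related* in a sense that plausibly means the investigational product. Section 5.1 lets the safety review be unblinded where appropriate, so an SRC conclusion could depend on the arm. Fixing the definition before unblinding would also prevent a later choice between tables that could differ as much as 0/8 and 4/8.

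Part of this stands: the term is undefined, and the source of the tabulated value is not named. If the Investigator simply records the presumption, the drug-related table would largely repeat the all-AE table, in both arms. The forced zero does not stand, because it needs a step that the plan never sets out.

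Tabulating the SRC's conclusion instead would be no improvement. Its scheduled review runs through Day 7 (5.2), while AEs are collected until 28 days after the last dose (9.7), so later events would have no scheduled SRC conclusion.

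**Conclusion.** No change to the plan is needed. Followed as written, it gives a causality value recorded blind for each AE and summarised in both arms, with an expected gap of zero when the drug has no effect. The 0/8 column is a hypothetical that requires arm-based recoding after unblinding. Even then only two descriptive summaries would be affected, and the all-AE and all-SAE summaries beside them would show the background rate.

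What remains is an undefined term of the kind a statistician settles when writing table specifications, in a protocol that defers such detail to a separate SAP. An analyst would sensibly use the blinded Investigator's assessment under one rule for both arms.

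The conclusion covers the protocol wording only, since the separate SAP is not in the text reviewed. It assumes that all eight placebo subjects are dosed and that recorded causality values are not altered once allocation is known. The sizes above rest on assumed AE rates and assumed shares left as related.

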### **9.4. Assessment of Severity**

The severity rating of an AE refers to its intensity. The severity of each AE will be graded according to the Toxicity Grading Scale for Healthy Adult and Adolescent Volunteers Enrolled in Preventive Vaccine Clinical Trials (<https://www.fda.gov/regulatory-information/search-fda->

[guidancedocuments/toxicity-grading-scale-healthy-adult-and-adolescent-volunteers-enrolledpreventive-vaccine-clinical](https://www.fda.gov/regulatory-information/search-fda-guidancedocuments/toxicity-grading-scale-healthy-adult-and-adolescent-volunteers-enrolledpreventive-vaccine-clinical)).

It is important to distinguish between serious and severe AEs. Severity is a measure of intensity whereas seriousness is defined by the criteria under [Section 9.1.2](#). An AE of severe intensity may not be considered serious.

## **9.5. Pregnancy or Drug Exposure during Pregnancy**

If a subject becomes pregnant during the study, administration of study drug is to be discontinued immediately.

Pregnancies must be reported within 24 hours of the Investigator's knowledge using the Sponsor's pregnancy form.

Pregnancy in itself is not regarded as an AE or SAE unless there is a suspicion that an investigational product may have interfered with the effectiveness of a contraceptive medication.

The outcome of all pregnancies (spontaneous miscarriage, elective termination, normal birth or congenital abnormality) must be followed up and documented even if the subject was discontinued from the study.

All reports of congenital abnormalities/birth defects are SAEs. Spontaneous miscarriages should also be reported and handled as SAEs. Elective abortions without complications should not be handled as AEs.

## **9.6. Laboratory Abnormalities**

The severity of each laboratory AE will be graded according to the Toxicity Grading Scale for Healthy Adult and Adolescent Volunteers Enrolled in Preventive Vaccine Clinical Trials (<https://www.fda.gov/regulatory-information/search-fda-guidancedocuments/toxicity-grading-scale-healthy-adult-and-adolescent-volunteers-enrolledpreventive-vaccine-clinical>).

To the extent possible, all laboratory abnormalities observed during the course of the study will be included under a reported AE term describing a clinical syndrome (e.g., elevated blood urea nitrogen and creatinine in the setting of an AE of "renal failure"). In these cases (e.g., an AE of renal failure), the laboratory abnormality itself (e.g., elevated creatinine) does not need to be recorded as an AE.

If a laboratory abnormality cannot be reported as a clinical syndrome, AND if the laboratory abnormality results in a therapeutic intervention (i.e., concomitant medication or therapy), or is judged by the Investigator to be of other clinical relevance, then the laboratory abnormality should be reported as an AE.

Subjects experiencing AEs or clinically significant laboratory abnormalities will be assessed and appropriate evaluations performed until all parameters have returned to baseline levels or are consistent with the subject's then-current physical condition.

## **9.7. Reporting Adverse Events**

All AEs, serious and nonserious, will be fully documented on the appropriate eCRF. For each AE, the Investigator must provide its duration (start and end dates or ongoing), intensity,

assessment of causality and whether specific action or therapy was required. All AEs occurring during this healthy-volunteer study will be presumed to be related to study drug unless occurring before the study therapy is initiated pending review by the SRC.

All AEs that occur from the signing of the informed consent form (ICF) until the first dose of study drug should be recorded on the AE eCRF page only if the event was related to a study procedure. All other AEs/findings prior to the first dose of study drug should be recorded as medical history on the applicable eCRF page. All AEs occurring from the first dose of study drug until 28 days after the last dose of study drug must be recorded on the AE eCRF.

All SAEs and Grade 4 AEs must be reported to the Sponsor within 24 hours of the Investigator's knowledge. All AEs occurring during this healthy-volunteer study will be presumed to be related to study drug unless occurring before the study therapy is initiated pending review by the SRC. This reporting should be done by faxing/emailing the completed SAE Report Form to the number provided on the SAE Report Form. After the EOS Visit, only new treatment-related SAEs need to be captured on the AE eCRF and reported to the Sponsor.

Investigators must follow subjects with AEs/SAEs until the event has resolved, the condition has stabilized, withdrawal of consent, the subject is lost to follow up or death OR until the EOS Visit, whichever occurs first. New and ongoing treatment-related SAEs should be followed beyond the EOS Visit. If the subject dies, this should be captured as the outcome of the AE unless no link between the AE and the subject death can be established, in which case the AE will be marked as ongoing and the death will be reported as a separate event.

If a subject is lost to follow up, this should be captured accordingly within the AE eCRF and on the follow up SAE report.

The Sponsor or designee is responsible for notifying the relevant regulatory authorities of applicable suspected unexpected serious adverse reactions (SUSARs) as individual notifications or through periodic line listings. It is the Principal Investigator's responsibility to notify the Institutional Review Board (IRB) or IEC of all SAEs that occur at his or her site. Investigators will also be notified of all unexpected, serious, and drug-related events (7/15 Day Safety Reports) that occur during the clinical trial. Each site is responsible for notifying its IRB or IEC of these additional SAEs.

## 10. STATISTICS

### 10.1. General Overview

#### 10.1.1. Method of Assigning Subjects to Treatment Groups

For each dosing group, 8 subjects will be randomized in a 3:1 ratio to receive an equal volume of rhu-pGSN or saline placebo during the treatment period. See [Section 7.11](#) for details regarding randomization.

#### 10.1.2. Data Collection and Analysis

Baseline characteristics, safety, PK, and development of ADAs will be summarized via summary statistics separately for each rhu-pGSN dose level; data for all placebo subjects will be pooled. Additional details will be provided in a separate Statistical Analysis Plan (SAP).

### 10.2. Sample Size and Power Calculations

Prior studies of rhu-pGSN evaluated 3 doses of rhu-pGSN in subjects hospitalized with CAP or COVID-19. To expand our understanding of possible rhu-pGSN toxicities in the absence of underlying disease, 24 healthy subjects will be administered 5 doses of rhu-pGSN at 6, 12, 18, and 24 mg/kg of body weight (6 subjects per dose group) and 8 healthy subjects (2 subjects per dose group) will be given the same volume on a weight basis of a visually indistinguishable 0.9% saline placebo to provide additional data to inform the safety and tolerability of rhu-pGSN.

[Table 5](#) presents the minimum sample size such that there is a 90% probability of observing at least 1 AE of a certain type if the TRUE underlying AE incidence is as specified.

**Table 5: Minimum Sample Size Calculations**

Sample Size	TRUE Underlying AE Rate
6 (each rhu-pGSN dose level)	32%
8 (pooled placebo)	25%
12	18%
18	13%
24 (pooled rhu-pGSN doses)	10%

With each sample size presented in [Table 5](#), if zero AEs of a certain type (e.g., SAEs) are observed, one could be "90% confident" that the TRUE underlying incidence for that AE is at most the percentage indicated in [Table 5](#). Thus with 24 healthy subjects, if no SAEs are observed, the probability is 90% that the true underlying incidence of SAEs in healthy subjects administered 5 doses of rhu-pGSN at 6, 12, 18, or 24 mg/kg of body weight is at most 10%.

### 10.3. Analysis Populations

No data will be excluded from the summary statistics and analyses, and missing data will not be imputed. All subjects given at least part of 1 dose of study drug will be included in the intention-to-treat analysis (full analysis set). As a sensitivity analysis, a per-protocol analysis set excluding subjects who missed doses and/or randomly discontinued the study before the primary Day 7 Visit will be analyzed. The expectation is that all analysis sets will be almost identical.

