### 5.2. Safety Review Committee

The safety data will be reviewed by a Safety Review Committee (SRC) comprised of at least 1 expert clinician, the Medical Monitor at the contract research organization, and the Sponsor's Chief Medical Officer.

Adverse events (AEs) will be categorized as "serious" according to the judgement of the site investigator as to whether the definition of SAE (section 9.1.2) is met and then reviewed and adjudicated by the SRC. The "severity" of an AE will be graded according to the Toxicity Grading Scale for Healthy Adult and Adolescent Volunteers Enrolled in Preventive Vaccine Clinical Trials. An individual patient will be discontinued permanently from study treatment if they experience any serious adverse event (SAE) or a severity Grade 3 or greater AE (including infusion reactions). Further study treatment and enrollment will be paused pending review by the SRC if there are two Grade 3 AEs, one Grade 4 AE, or one SAE. The study will only be resumed if the SRC unanimously judges the AEs as unrelated to study treatment and procedures after consultation with regulatory and outside experts as needed.

The SRC will review safety data (including lab tests) through the Day 7 visit for each dosing arm to determine if it is safe to initiate the next cohort according to the safety criteria for stopping doses ([Section 5.3](#)).

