### 5.3. Safety Criteria for Stopping Doses

Dosing of rhu-pGSN may be stopped during the study at the discretion of the SRC. All AEs occurring during this healthy-volunteer study will be presumed to be related to study drug unless occurring before the study therapy is initiated pending review by the SRC.

An individual patient will be discontinued permanently from study treatment if they experience any serious adverse event (SAE) or a severity Grade 3 or greater AE (including infusion-related reactions) regardless of causality.

Further study treatment and enrollment will be paused pending review by the SRC if any patient dies or there are two Grade 3 AEs, one Grade 4 AE, or one SAE. The study will only be resumed if the SRC unanimously judges the death or AEs as unrelated to study treatment and procedures after consultation with regulatory and outside experts as needed.

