### **5.3.1. Management of rhu-pGSN Infusion-Related Reactions**

In general, doses should only be temporarily interrupted for Grade 1 or 2 AEs, but treatment to control symptoms should be provided, if applicable. The infusion can be restarted at a slower rate once symptoms have dissipated. If symptoms recur, the infusion will be permanently discontinued. If a subject develops a Grade 3-4 IRR:

- The infusion should be stopped immediately, and the infusion tubing should be disconnected from the subject.
- The subject should receive appropriate treatment with an antihistamine and/or acetaminophen (paracetamol) and/or methylprednisolone (or equivalent) and, if necessary, further medications (i.e., epinephrine, bronchodilator).
- The subject may not receive further infusions of study therapy.

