### **7.4. Study Drug Administration**

rhu-pGSN is administered via IV push  $\leq$ 20 mL/minute. A total of 5 doses of rhu-pGSN will be administered to participating subjects at 0, 12, 36, 60, and 84 hours. Dose 1 is time 0; a window of  $\pm$ 2 hours will be allowed around dosing times for the 2nd and 3rd doses, and  $\pm$ 4 hours for the last 2 doses.

Subjects are to be monitored for administration site reactions during an infusion and for 1 hour after its completion. Infusion site reactions will be recorded as AEs using the appropriate coding terms on the eCRF.

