**Table 4: Schedule of Assessments**

	Outpatient	Inpatient	Inpatient	Inpatient	Inpatient	Discharge	Outpatient	Outpatient
Visit	Screening	Baseline/ Randomization /Treatment	Treatment/Follow-Up Days					EOS Visit
Day	-6 weeks to 0	1	2	3	4	5	7 ±1	28 ± 3
Informed consent	X							
Eligibility assessment	X							
Demographics	X							
Medical history	X							
Blood or urine pregnancy test a	X b							X
Physical exam (incl. height and weight)	X							
Vital signs c	X	X	X	X	X	X	X	
Blood/urine for safety laboratory analyses d	X b						X	X
Adverse events e		X	X	X	X	X	X	X
Review of Systems/Symptoms e	X	X	X	X	X	X	X	X
Study drug administration f		X/X (0 and 12 hours)	X (36 hours)	X (60 hours)	X (84 hours)			
Blood sampling for pGSN levels g		X (Dose #1)			X (Dose #5)	X (24 hours after Dose #5)	X	X

	Outpatient	Inpatient	Inpatient	Inpatient	Inpatient	Inpatient	Discharge	Outpatient	Outpatient
Visit	Screening	Baseline/ Randomization /Treatment	Treatment/Follow-Up Days						EOS Visit
Day	-6 weeks to 0	1	2	3	4	5	7 ± 1	28 ± 3	
Anti-rhu-pGSN antibody sampling		X							X
Concomitant medications	X	X	X	X	X	X	X	X	

Abbreviations: AEs=adverse events; ALT=alanine aminotransferase; aPTT=activated partial thromboplastin time; AST=aspartate aminotransferase; CBC=complete blood count; CPK=creatine phosphokinase; EOS=end of study; PK=pharmacokinetic; PT=prothrombin time

a Perform a serum or urine pregnancy test for female subjects unless they have had a hysterectomy.

b If performed more than 36 hours before initiation of study drug, the test must be repeated within this time frame.

c Record blood pressure, oral temperature, respiration rate, and heart rate. To be measured during infusions at the following time points: pre-infusion, every 15 minutes after the start of infusion, at the end of infusion, and 30 minutes after the end of infusion.

d Safety labs include collection of blood for a CBC, PT, aPTT, creatinine, bilirubin, alkaline phosphatase, CPK, AST, and ALT levels and collection of urine for drug screening (e.g., amphetamines, benzodiazepines, cannabinoids, cocaine, and opiates) and urinalysis (dipstick: glucose, protein, red blood cells, white blood cells).

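### Read literally, the per-protocol set drops every subject stopped for toxicity before Dose #5, so it cannot test the robustness of the adverse event results

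*Combined protocol and SAP*

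**What the plan says.** Section 10.3 defines two analysis sets. The full analysis set holds everyone who received any study drug, even a partial dose. The second is a sensitivity set: "a per-protocol analysis set excluding subjects who missed doses and/or randomly discontinued the study before the primary Day 7 Visit will be analyzed". The synopsis repeats the rule: "As a sensitivity analysis, a per-protocol analysis set excluding subjects who missed doses". Section 10.3 adds that the sets should turn out nearly the same. It does not define a missed dose and does not say which endpoints the per-protocol set serves. Section 10.1.2 leaves further detail to a separate SAP, which is not part of the text reviewed here.

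The stopping rules are in Section 5. Under Section 5.2 a subject "will be discontinued permanently from study treatment if they experience any serious adverse event (SAE) or a severity Grade 3 or greater AE". Section 5.3 repeats this with the words "or a severity Grade 3 or greater AE (including infusion-related reactions) regardless of causality". After a Grade 3-4 infusion reaction, Section 5.3.1 says: "The subject may not receive further infusions of study therapy". Section 5.3 also has a study-level rule: "Further study treatment and enrollment will be paused pending review by the SRC if any patient dies or there are two Grade 3 AEs", with a single Grade 4 AE or SAE as further triggers.

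On dosing, Section 7.4 states: "A total of 5 doses of rhu-pGSN will be administered to participating subjects at 0, 12, 36, 60, and 84 hours". The primary endpoint (Section 4.2.1) is the incidence and severity of AEs, whatever their cause.

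**The concern.** A sensitivity analysis is useful only if it could disagree with the main analysis for a reason unrelated to how its subjects were chosen. Here the exclusion rule and the stopping rules interact. A severe or serious event leads to a treatment stop, the stop leads to undelivered doses, and undelivered doses lead to exclusion. For events before Dose #5, membership of the set therefore depends on the primary outcome itself.

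A per-protocol AE table built this way would show none of these events, whatever their true rate. Someone reading it beside the full-set table could take it to mean that subjects who followed the protocol had no severe toxicity, when such subjects were removed by rule.

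**Working it through.** The plan gives no figure on this point, so there is none to reproduce. The check sets the rules side by side and then counts.

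**1. Does the exclusion reach toxicity stops?** The Section 10.3 rule has two limbs: missing doses, and leaving the study at random before Day 7. The word for random attaches only to leaving the study. The missed-dose limb carries no reason.

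**2. Which events lead to a missed dose?** Doses are scheduled at 0, 12, 36, 60 and 84 hours. If treatment stops after dose k, the number of doses not given is 5 − k:

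| Stop after dose | Hour | Doses not given |
|---|---|---|
| 1 | 0 | 4 |
| 2 | 12 | 3 |
| 3 | 36 | 2 |
| 4 | 60 | 1 |
| 5 | 84 | 0 |

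A stopping event at or after any of the first four doses, but before Dose #5, leaves at least one dose undelivered. Events starting at or after Dose #5 in subjects who received all doses stay in the set. Whether a Dose #5 infusion broken off part-way counts as missed is undefined.

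**3. What does the set then show?** Let x of n treated subjects have a stopping event before Dose #5, with no other exclusions. The full set shows x/n and the per-protocol set shows 0/(n − x). The difference is x/n, the whole observed rate. For these events the sets agree only when x = 0. Group sizes are from Section 10.2; the event counts are assumed.

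| Group | x | Full analysis set | Per-protocol |
|---|---|---|---|
| One dose level, n = 6 | 1 | 1/6 = 16.7% | 0/5 |
| One dose level, n = 6 | 2 | 2/6 = 33.3% | 0/4 |
| Pooled active, n = 24 | 1 | 1/24 = 4.2% | 0/23 |
| Pooled active, n = 24 | 2 | 2/24 = 8.3% | 0/22 |
| Pooled placebo, n = 8 | 1 | 1/8 = 12.5% | 0/7 |

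A single Grade 3 AE that is not serious does not trigger the study pause, so the x = 1 rows can arise in an otherwise uninterrupted cohort. The documents give no expected rate for these events in healthy volunteers, so no probability is attached to the rows.

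**4. What else leaves with the subject?** Exclusion is by subject, not by event. The Table 4 row "Blood/urine for safety laboratory analyses" is marked at screening, Day 7 and Day 28 only, so a scheduled post-dose laboratory result cannot itself cause a stop before Dose #5. But when a subject is removed for a clinical event, their Day 7 and Day 28 laboratory results and any later AEs go too.

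**5. Safety pause.** Dosing windows are ±2 hours for Doses 2 and 3 and ±4 hours for Doses 4 and 5 (Section 7.4). A pause could make other subjects still on treatment miss doses and leave the set. Their exclusion would not follow from their own outcome, and how many are at risk depends on whether a cohort is dosed together, which is not stated.

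**The case against.** The strongest reply is that the text permits this exclusion without clearly requiring it. A subject whose later doses were withheld under Section 5.3 has followed the protocol, so a withheld dose may not be a missed one. The reference to random discontinuation and the expectation of near-identical sets suggest that only uninformative departures were meant. This stands as a reason for caution about intent. It does not remove the problem, because the wording of the missed-dose limb does not carry that intent.

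Second, no endpoint is assigned to the set. PK parameters after Dose #5 are a natural use for subjects who received all five doses, and there the exclusion is sensible. This stands: the concern applies only if AEs are tabulated on the set.

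Third, every event is still reported. The full analysis set keeps all treated subjects, Section 10.4.1 summarises SAEs, deaths and AEs leading to discontinuation, and nothing in Sections 5.2 and 5.3 ties the Safety Review Committee's review to this set. This stands too, and it limits the severity.

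A reader might infer more than the documents support:

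- That the per-protocol set can contain no SAE or Grade 3+ AE at all. It can, if the event starts at or after Dose #5.
- That the main safety conclusion is biased. It rests on the full analysis set.
- That the zero-event statement in Section 10.2 would be made on the reduced set and mislead. Section 10.2 ties its example to all 24 active subjects, and nothing extends it to the per-protocol set.
- That recurrent Grade 1-2 infusion symptoms lead to exclusion in the same way. Section 5.3.1 ends the infusion in that case but does not clearly bar later doses, so this is not relied on.

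Section 5.6 says participation may be discontinued for these events, where Sections 5.2 and 5.3 say treatment will be. The first concerns the study and the second concerns treatment, so the point does not depend on it, but the passages should be reconciled.

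**Conclusion.** The point holds in a limited form and is minor. Taken literally, Section 10.3 and the synopsis remove from the per-protocol set every subject stopped for an SAE, a Grade 3+ AE or a Grade 3-4 infusion reaction before Dose #5, together with all of that subject's data. If the set is used for AE summaries, its count of these events is zero by construction and it cannot test the primary safety result. One such event is 1/6 against 0/5 at a dose level, or 1/24 against 0/23 pooled.

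This rests on three assumptions: that a dose withheld by rule counts as missed, that the set is applied to AEs, and that at least one such event occurs. The documents settle none of them. The effect is confined to the sensitivity analysis.

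**What to change.** State in Section 10.3, the synopsis and the SAP that all safety and AE summaries use all treated subjects only, and that the per-protocol set is for PK (for example, Dose #5 parameters) or other non-safety summaries. Define a missed dose in the same place, including whether an interrupted dose counts. Reconcile the opening statement of Section 10.3, that nothing is excluded from the analyses, with the per-protocol exclusion.

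If a per-protocol safety table is still wanted, doses withheld for an AE, a stopping rule or a safety pause should not count as missed, and the table should be labelled as having outcome-dependent membership. This is the weaker option, because it tilts the set the other way. With 2 toxicity stops and 2 subjects missing doses for other reasons among 24 (assumed), the full set gives 2/24 = 8.3% and this table 2/22 = 9.1%.

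The cost is a few sentences in the protocol, matched in the SAP. No data, subjects, dosing rule or stopping rule change.
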